### **Inclusion Criteria**

1. Were established smokers (smoked at least 100 cigarettes in their lifetime and currently smoked cigarettes some or all days).
2. Were 21 years of age or older (the legal age of tobacco purchase in the US).
3. Had not completed the cognitive interview during message development.
4. Rated their agreement with the following statement as at least 50 out of 100: “The substance nicotine causes cancer.”

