### **Study Statistics**

- a. Primary outcome variable
  1. Change in Accuracy of Belief That Nicotine Causes Cancer
  2. Change in Relative Harm Beliefs Regarding E-cigarettes
  3. Change in Relative Harm Beliefs Regarding NRT
  4. Change in Relative Harm Beliefs Regarding Very Low Nicotine Cigarettes
  5. Change in Inferential Beliefs Regarding Smokeless Tobacco
  6. Change in Inferential Beliefs Regarding Cigarillos
  7. Change in Beliefs About Intention to Switch Products
- b. Statistical plan: Stata version 15 was used for all statistical analyses. Fisher’s exact tests were used to assess balancing across conditions by categorical variables to account for small cell size (e.g. cell sizes with  $n < 10$ ). ANOVAs were used to assess differences in continuous variables to assess balancing. Analysis of Covariance (ANCOVA) was used to identify differences by condition in agreement that nicotine causes cancer, controlling for pre-exposure belief (RQ1a) and intention to switch to a noncombustible controlling for pre-exposure intention (H2). Post hoc testing was used to assess pairwise differences between conditions when the covariate for condition was significant at  $p < .05$ , comparing each condition to the condition with both components of coherence. Sidak’s adjustment was used to control the type I error. Research questions and hypotheses with relative harm outcomes (RQ1b-d, H1a-b) were dichotomized due to failure to meet the assumptions of ANCOVA and were analyzed using logistic regression. Responses “much more harmful,” “somewhat more harmful,” and “not less or more harmful” were considered high relative harm perceptions. Responses “somewhat less harmful” and “much less harmful” were considered low relative harm perceptions. Unadjusted regressions as well as regression adjusted for pre-message exposure beliefs and product use were run. Inclusion of pre-exposure beliefs as a covariate in the models for NRT and cigarillos resulted in unstable odds ratios due to near perfect

prediction. Pre-exposure beliefs were thus dropped in these models. Marginal estimates for each condition were calculated and plotted for all adjusted models.

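### NRT and cigarillo models drop the pre-exposure belief that a penalised fit could keep, and a null low/high result needs a stated limit

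*Combined protocol and SAP*

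**What the plan says.** Part a of Study Statistics lists seven primary outcomes. Two of them are "Change in Relative Harm Beliefs Regarding NRT" and "Change in Inferential Beliefs Regarding Cigarillos".

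Part b says the relative harm outcomes (RQ1b-d and H1a-b, apparently primary outcomes 2 to 6) "were dichotomized due to failure to meet the assumptions of ANCOVA and were analyzed using logistic regression". The neutral answer and the two "more harmful" answers "were considered high relative harm perceptions"; the two "less harmful" answers form the low class. Each outcome has an unadjusted model and one adjusted for pre-message belief and product use.

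Two products are exceptions: "Inclusion of pre-exposure beliefs as a covariate in the models for NRT and cigarillos resulted in unstable odds ratios", put down to near perfect prediction. The response was: "Pre-exposure beliefs were thus dropped in these models". Product use appears to stay in those two models. No penalised or exact fit is mentioned, and no analysis using all five answer levels is described.

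**The concern.** An outcome named as change is normally analysed with the starting value in the model. For NRT and cigarillos no described model that was kept contains it. Near perfect prediction says that the covariate removed was a very strong predictor of the post-message answer, so removing it may cost precision. The odds ratios for these two products also no longer condition on starting belief, while those for e-cigarettes, very low nicotine cigarettes and smokeless tobacco do. The five adjusted odds ratios should not be read side by side as like quantities.

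The Benefits section says the findings should help choose messages that improve accuracy of beliefs about different products. A null result for NRT or cigarillos could be taken to mean that the message did nothing. It could instead reflect lost precision or, for any of the five products, movement inside a class that the cut cannot register.

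**Working it through.** **Inputs.** From the documents: four arms at 1:1:1:1 (Study Procedures); a test of condition at .05, followed by pairwise tests "comparing each condition to the condition with both components of coherence" (Study Statistics), taken here to apply to the logistic models too; the low/high cut. Assumed: 100 or 200 per arm, baseline shares, crossing rates, two-sided tests, one arm differing, no product-use covariate. The plan states no sample size, power or distribution, so there is no figure of its own to reproduce.

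**Step 1: what the model without the baseline compares.** Let π be the share low before the message, d the chance of crossing from low to high, and u the chance of crossing from high to low. Then

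P(low after) = π(1 − d) + (1 − π)u.

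- Cigarillo-like, π = 0.08, d = 0.03, u = 0.01 vs 0.06: 0.0776 + 0.0092 = 0.087 vs 0.0776 + 0.0552 = 0.133.
- NRT-like, π = 0.85, d = 0.01, u = 0.10 vs 0.30: 0.8415 + 0.015 = 0.857 vs 0.8415 + 0.045 = 0.887.

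The first term is the same in both arms. It adds variation but no contrast, and the baseline covariate would absorb it.

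**Step 2: when the ordinary fit breaks down.** With N people in all, the chance that nobody crosses from low to high, so that the baseline odds ratio has no finite estimate, is (1 − πd)^N. Instability short of this is also possible with one or two crossings.

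**Step 3: simulated power.** "Dropped" omits the baseline; "Firth" keeps it, with a penalised likelihood-ratio test.

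| Setting (π; d; u) | Arms × per arm | (1 − πd)^N | Dropped | Firth |
|---|---|---|---|---|
| Cigarillo-like (8%; 3%; 1 vs 6%) | 2 × 100 | 0.9976^200 = 0.62 | 19% | 41% |
| same | 2 × 200 | 0.9976^400 = 0.38 | 33% | 72% |
| NRT-like (85%; 1%; 10 vs 30%) | 2 × 100 | 0.9915^200 = 0.18 | 13% | 25% |
| same | 2 × 200 | 0.9915^400 = 0.03 | 16% | 36% |
| NRT-like, more crossing (80%; 2%; 10 vs 35%) | 4 × 200 | 0.984^800 < 0.001 | 23% | 65% |
| Cigarillo-like, more crossing (10%; 5%; 2 vs 7%) | 4 × 200 | 0.995^800 = 0.02 | 25% | 61% |

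The two-arm rows rest on 400 runs each (standard error at most √(0.25/400) = 2.5 points), the last two rows on 6,000.

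The last two rows need care. Expected crossings from low to high are 800 × 0.016 = 12.8 and 800 × 0.005 = 4, so an ordinary logistic model would usually have fitted. When it was run with the baseline kept, its power was 68–69% and 63–66%. Those rows show what baseline adjustment is worth, not what penalisation rescues after a breakdown.

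In four-arm settings at 100 to 200 per arm where instability is frequent, dropped vs Firth ran from about 5% vs 5% to 28% vs 67%. With the fewest crossings there was no gain at 100 per arm (4–6% vs 3–6%), and at 200 per arm a gain that left power low (5–8% vs 10–19%).

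If one class is small and prediction is weaker (92% low before; 5% crossing down; 30 vs 60% crossing up), four arms of 200 give 11% vs 15%.

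**Step 4: type I error.** Firth is conservative when crossings are few: about 2% in four-arm settings at 100 per arm. In the sparsest two-arm setting it was 0.75% at 100 per arm and 3.5% at 200.

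**Step 5: the limit on a null low/high result.** Take shares, from "much less" to "much more" harmful, of 2/6/50/25/17% in one arm and 2/6/65/18/9% in another. The low share is 2 + 6 = 8% in both. The mean score on 1 to 5 is 0.02 + 0.12 + 1.50 + 1.00 + 0.85 = 3.49 in the first and 0.02 + 0.12 + 1.95 + 0.72 + 0.45 = 3.26 in the second. The binary analysis has nothing to detect, although answers differ. This follows from the cut itself; the shares only illustrate it.

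**The case against.** The strongest reply is that little is wrong. The plan discloses the cut, the reason for it, the covariate removed and why. Randomization protects the comparison without the baseline. Near perfect prediction may mean that few people changed class, and a penalised fit cannot create information that is not there. Marginal estimates are reported for every adjusted model, and on that scale products can be set side by side more readily than on the odds ratio scale. All of this stands, and it is why the point is minor.

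A reader might infer more than the documents support:

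- *That the NRT and cigarillo comparisons are biased or invalid.* They are not. The loss is in precision and in comparability of odds ratios.
- *That a penalised fit would nearly triple power.* The settings giving 23% vs 65% and 25% vs 61% are mostly ones where the ordinary model fits, which is not the situation reported.
- *That dichotomising was an error and an ordinal model should replace it.* Failed ANCOVA assumptions do not force two classes, but the cut is a coherent accuracy threshold for e-cigarettes, NRT and smokeless tobacco. No form wins everywhere: under assumed shares with 200 per arm, movement from neutral to "somewhat less" gives the binary test 57% and the ordinal test 17%, while movement from "somewhat less" to "much less" gives 5% and 61%.
- *That the cut was chosen after seeing results.* The wording is compatible with that, but no date is given.

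**Conclusion.** The point holds as a minor one. For two of the seven primary outcomes the plan gives up a strong baseline predictor for a numerical reason that a penalised likelihood addresses. Nothing reported is invalidated. The gain ranges from none to more than double the power, and the documents cannot place the trial in that range: they give no sample size or answer distribution, and do not say whether the instability came from few crossings or from a small class, or whether the baseline entered as two classes or five levels. All power figures rest on assumed rates and omit product use.

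Separately, and without any assumption, a null low/high result on any of the five outcomes shows only that no difference in crossing the cut was found. It does not show that beliefs stayed put.

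**What to change.** 1. Refit the NRT and cigarillo low/high models with condition, pre-exposure belief and product use by Firth-type penalised likelihood. Use penalised likelihood-ratio tests and profile intervals, and report the results beside the fit without pre-exposure belief.
2. Report counts at all five answer levels, by condition, before and after the message. These also show whether few crossings or a small class caused the instability.
3. State that a null binary result means no difference in crossing the low/high cut. An ordinal or less/same/more model is optional and descriptive only; the binary result stands if they disagree.

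The cost is two refits, one table and a sentence of wording, all from data already held. The downside is that the Firth test is conservative when crossings are very few, so a null from it should not be read as stronger evidence than the present fit gives.

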## Study Procedures

Participants were recruited online using Amazon Mechanical Turk. After clicking on the tasks, participants first consented to answering questions on a screening questionnaire to determine eligibility. Eligible participants then read an informed consent for the experiment. After agreeing to participate, participants were asked questions about their sociodemographic characteristics, beliefs, behaviors, and behavioral intentions about different tobacco products. Participants were then randomized to view one of four messages using a 1:1:1:1 ratio using the “evenly present elements” option in Qualtrics. One message had only a causal alternative, one had only a reason the misinformation about nicotine causing cancer came to be believed, one have both strategies, and one had neither strategy. As randomization

was conducted in Qualtrics, both experimenters and participants were blinded to randomization. After message exposure, participants answered questions about the message and their beliefs and intentions to use different tobacco products. The survey took between 10-15 mins to complete. The study protocol was approved by the Institutional Review Board at the Johns Hopkins Bloomberg School of Public Health on August 4, 2021 (IRB00015120). No participants were removed while the study was ongoing, but responses that showed signs of being repeat responders or bots (according to metrics from survey platform Qualtrics) were later dropped from analysis.

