#### Risks

- a. Risks were minimal and included boredom of discomfort from answering survey questions.
- b. To mitigate this risk, participants read in the informed consent that they were free to skip any questions they didn't want to answer or quit their participation at any time.
- c. There were no unanticipated problems or deviations during data collection.

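### NRT and cigarillo models discard the pre-exposure belief because the logistic fit was unstable: no bias, but an avoidable and unquantifiable loss of power on two of seven primary outcomes

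*Combined protocol and SAP*

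**What the plan says.** Study Statistics, item a, lists seven primary outcomes, each worded as a change. Two of them are "Change in Relative Harm Beliefs Regarding NRT" and "Change in Inferential Beliefs Regarding Cigarillos".

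Item b dichotomises the five relative-harm outcomes into high and low perceived harm and analyses them by logistic regression: "Unadjusted regressions as well as regression adjusted for pre-message exposure beliefs and product use were run". It then makes an exception: "Inclusion of pre-exposure beliefs as a covariate in the models for NRT and cigarillos resulted in unstable odds ratios due to near perfect" prediction (the sentence runs over a page break), followed by "Pre-exposure beliefs were thus dropped in these models". No penalised, exact or risk-difference method is named for these two products. The paragraph ends: "Marginal estimates for each condition were calculated and plotted for all adjusted models".

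Under Study Procedures, the baseline questions come first. Participants were then "randomized to view one of four messages using a 1:1:1:1 ratio".

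**The concern.** When a baseline covariate almost determines the outcome, maximum-likelihood logistic regression can produce very large or undefined coefficients. The usual remedy is an estimator that tolerates sparse cells. The plan removed the covariate instead, although the same paragraph uses exact tests for small cells in its balance checks.

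Two things follow. First, the NRT and cigarillo analyses forgo precision that data already collected could supply, so a null result for either product is harder to interpret than one for the other three. Second, the five adjusted odds ratios are on different footings: three are conditional on baseline belief and product use, two on product use alone. Odds ratios are non-collapsible, so the same effect gives a different odds ratio under each model even with no bias. The plotted marginal estimates for NRT and cigarillos also come from models without baseline.

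**Working it through.** **What can be reproduced.** The plan states no sample size, power or event rate, so there is no figure to reproduce. Every prevalence, transition rate and sample size below is an assumption.

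**Notation.** q = proportion with low perceived harm at baseline; s = proportion of those who stay low; m = proportion of the rest who move to low; p = qs + (1 − q)m = proportion low after the message. The baseline is treated as binary.

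**Step 1: precision lost on the risk-difference scale.** The share lost is about φ², with φ the pre/post correlation:

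φ² = q(1 − q)(s − m)² / [p(1 − p)]

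- NRT-like grid (q 60–90%, s 99–99.9%, m 10–60%; 90 points): 26% to 88%, above one half at 58% of points. Lower end: q = 0.6, s = 0.99, m = 0.6 gives p = 0.834 and 0.24 × 0.39² / (0.834 × 0.166) = 0.26.
- Cigarillo-like grid (q 3–20%, s 95–99%, m 2–10%; 75 points): 19% to 90%, above one half at 61% of points. Lower end: q = 0.03, s = 0.95, m = 0.10 gives p = 0.1255 and 0.0291 × 0.85² / (0.1255 × 0.8745) = 0.19.
- Outside the grids: q = 0.02, s = 0.99, m = 0.20 gives p = 0.2158 and 0.0196 × 0.79² / (0.2158 × 0.7842) = 0.07.

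**Step 2: power.** Four arms, overall 3-df test of condition at 5%, 4,000 runs per scenario (Monte Carlo standard error at most √(0.25/4000) = 0.8 points). Logistic regression without baseline (likelihood-ratio test) is compared with Firth regression including baseline (penalised likelihood-ratio test). Cells show power without / with baseline.

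| | q | s | m: one arm / other three | 100 per arm | 200 per arm | 300 per arm |
|---|---|---|---|---|---|---|
| A | 60% | 99.9% | 35% / 20% | 15% / 31% | 25% / 59% | 34% / 76% |
| B | 75% | 99.9% | 60% / 40% | 17% / 26% | 31% / 52% | 44% / 70% |
| C | 12% | 99% | 12% / 5% | 20% / 37% | 34% / 69% | 49% / 87% |
| D | 5% | 99% | 17% / 8% | 37% / 45% | 66% / 79% | 86% / 95% |

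The gain runs from 8 points (D, 45 − 37) to 42 points (A, 76 − 34). A separate two-arm simulation (600 runs, Wald tests) gave gains of 7 to 42 points.

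**Step 3: do these scenarios produce the reported instability?** With 800 participants, the chance that nobody moves from low to high harm is (1 − q(1 − s))^800: A 0.9994^800 = 62%, B 0.99925^800 = 55%, C 0.9988^800 = 38%, D 0.9995^800 = 67%. The simulations had an empty baseline-by-outcome cell in 61%, 56%, 39% and 67% of runs.

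**Step 4: bias and type I error.** The mean risk difference without baseline was within 0.2 percentage points of the truth in every four-arm case. Type I error was 4.2% to 5.1% for Firth. It was 5.1% to 8.6% for a linear model with robust standard errors, worst in C at 100 per arm (8.6%, falling to 5.9% at 300).

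**Step 5: the odds-ratio scale.** In scenario A, among those starting with high perceived harm, the odds ratio is (0.35/0.65)/(0.20/0.80) = 2.15. Without baseline, p = 0.5994 + 0.14 = 0.739 against 0.5994 + 0.08 = 0.679, giving (0.739/0.261)/(0.679/0.321) = 1.34. The pairs for B, C and D are 2.25 and 1.58, 2.59 and 1.49, 2.36 and 1.86.

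**The case against.** The strongest reply is that the plan discloses the exception, names both products and gives the reason. Unadjusted regressions were run for all five products, so a common basis already exists. A randomised comparison without baseline is valid, and omitting Firth regression is not an error. All of this stands, and it is why the point is about efficiency and presentation and not about validity. It does not recover the lost precision.

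A second reply concerns size. The plan does not say how the baseline belief was coded or which odds ratios were unstable; sparse levels of a five-category item could be the cause. With q = 2%, s = 99% and m = 10% or 20%, the precision loss is 15% or 7%, yet with 800 participants an empty cell occurs in 0.9998^800 = 85% of samples. For an NRT-like case with q = 60–90%, s = 99.9% and m = 80%, the loss is 13–17%. So severe instability can go with a modest loss, and the shares of grid points above one half reflect where the grids stop. Nothing in the documents supports the assumed baseline prevalences. This stands: it cannot be said that most of the precision was lost.

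Two further limits also stand. Product use stays in the reduced models and was not simulated, so the gains in the table lean high. The plan describes the overall test of condition as a gate in connection with ANCOVA and does not say that it applied to the logistic models.

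Finally, the analyses are already done, and another estimator adds a further fit across seven primary outcomes. That is a reason to label the refit post hoc, not to leave it out.

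**Conclusion.** The concern holds and should be fixed, although it does not invalidate the trial. Two of seven primary outcomes are analysed without the baseline that the plan intended to use, because of a fitting problem that has a standard remedy.

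The test of no effect and the marginal contrast remain unbiased by randomisation. The direction of the cost, lower power, follows from near-perfect prediction. Its size cannot be determined for this trial: under assumed inputs the precision loss runs from 7% to 90%, and the simulated power loss from 7 to 42 points. These figures rest on a binary baseline, ordinary unpenalised logistic regression (the plan says only logistic regression) and the assumed sample sizes and transition rates. The incomparability of the five adjusted odds ratios does not depend on those inputs being right in detail.

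**What to change.** 1. Refit the NRT and cigarillo models with condition, pre-exposure belief and product use by Firth penalised logistic regression, testing condition by penalised likelihood ratio. Label the refit post hoc and show it beside the reported models.
2. Report baseline-adjusted marginal risk differences against the combined message for all five products, so that they share one basis.
3. Use a linear model of the low-harm indicator on the same terms, with robust standard errors, as a check only. It should not stand alone if the sparse cell is very small.
4. Until the refit is available, label the NRT and cigarillo odds ratios as adjusted for product use only. State how the pre-exposure belief was coded.
5. Report how many participants skipped the pre-exposure item. The Risks section says that "they were free to skip any questions", and those who did so drop out of the adjusted fit.

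The cost is revised wording and a re-run on data already held. Firth estimation shrinks estimates slightly: standardised risk differences stayed within 0.2 points of the truth in the simulations. The linear check is mildly anti-conservative with sparse cells.

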#### Risks

- a. Risks were minimal and included boredom of discomfort from answering survey questions.
- b. To mitigate this risk, participants read in the informed consent that they were free to skip any questions they didn't want to answer or quit their participation at any time.
- c. There were no unanticipated problems or deviations during data collection.

#### Benefits

- a. Participants did not participate directly from being in the study. Findings can help to inform what kind of messaging might be helpful to adults who smoke in order to increase belief accuracy about different tobacco products and increase intention to quit to a less harmful noncombustible product.

#### Payment and Remuneration

- a. Participants were paid \$5.00 for completing the survey. Participants who were eligible but did not fully complete the survey were still paid.

#### Costs

- a. No costs were associated with participation.

